Aim 1: To determine the impact of telephone delivered Problem-Solving Therapy on disability in GWV with GWI. H1: Among Veterans with GWI, telephone delivered Problem-Solving Therapy will produce greater improvement in disability as compared to telephone delivered health education.

Aim 2: To determine the effect of Problem-Solving Therapy on problem-solving ability in GWV with GWI. H2a & H2b: Among Veterans with GWI, telephone delivered Problem-Solving Therapy will produce greater improvement in (H2a) self-reported problem-solving ability (measured with the Problem-Solving Inventory) and (H2b) objective problem-solving ability (measured with a neuropsychological battery) as compared to telephone delivered health education.

H2c & H2d: Improvement in (H2c) self-report problem-solving ability and (H2d) objective problem-solving ability will mediate the effect of telephone delivered Problem Solving Therapy on disability.

Exploratory Aim 3: To determine the effect of Problem-Solving Therapy on other symptoms of GWI. Problem-Solving Therapy may help GWV with GWI better compensate for other symptoms (e.g. avoid over exertion) which may improve other symptoms of GWI.

Exploratory H3a – H3b Among Veterans with GWI, telephone delivered Problem-Solving Therapy will produce greater improvement in (H3a) self-reported pain and (H3b) fatigue as compared to telephone delivered health education.

Study Population

We will screen up to 2,000 Veterans to obtain a final sample of up to 300 Veterans from the Gulf War who screen positive for GWI.

Inclusion:

- (a) deployed to first Gulf War and meets Kansas definition for GWI (see definition in measures section);
- (b) scores at least a half a standard deviation worse than the mean on the World Health Organization Disability Schedule (WHO-DAS II).

Exclusion:

- (a) current suicidal/homicide intent or plan assessed by The Columbia Suicide Severity Rating Scale, schizophrenia or current psychotic symptoms
- (b) self-reported diagnosis of a degenerative brain disorder or serious psychiatric or medical illness which may limit generalizability of the findings, limit safety or account for the symptoms of GWI.

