Once potential participants are identified, introduction letters will be mailed to their addresses. Approximately after two weeks of mailing the introduction letter to Veterans, research staff will contact potential participants to inform them about the study, obtain verbal consent for and conduct initial screenings over the phone. For Veterans who contact us over the phone or in-person, (e.g., after reading a posted flyer), we will obtain verbal consent for and conduct initial screenings in person or over the phone.

If a Veteran is screened as eligible to participate in the study, a date and time will be scheduled for the Veteran to come into one of the three study sites (East Orange VA, Canandaigua VA or Bedford VA) to be consented into the study and complete the baseline questionnaires and neuropsychological assessments.

b. Sessions

Once consented and baseline assessments (described below) are completed, therapy sessions will be scheduled with a Study Provider from the East Orange VA. Study providers will be a licensed provider, e.g., psychologist, nurse, social worker, or a trainee e.g., working under a licensed provider, at the East Orange VA. A Study Provider from the East Orange VA will provide the sessions via phone with all participants from all VA sites (East Orange VA, Canandaigua VA, and Bedford VA). We will have a standardized assessment regimen that all Study Providers will adhere to. Therapy sessions will be scheduled weekly, and may be adjusted to accommodate the Veteran's schedule and/or needs.

The telephone sessions with the Study Provider will generally be 1 hour. Most telephone sessions will be voice recorded and transcribed for quality assurance, i.e., fidelity to study protocols, length of sessions, engagement of participants. Coding of telephone sessions will occur by our off site collaborators once proper approvals are in place (i.e., DUA).

Study Arms

Veterans will be randomized either to the PST (treatment) or Health Education group (control).

If randomized to the PST (treatment):

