We will mail or provide written questionnaires to all participants before or after the 4th session and also before or after 6 months post-treatment (see Table 1). All questionnaires will also be returned to the East Orange VA. Participants who wish, may also complete the questionnaires over the phone with a study staff member at a date/time that is convenient for the participant.

Qualitative Interviews

Participants may be asked to participate in 2 qualitative interviews. The qualitative interview will be conducted via phone by a study staff member from one of the sites at a date/time convenient for the participant after the baseline assessment and after the 12th session assessment. Participants will be asked about their perceptions of GWI and intervention methods. The qualitative interviews will be recorded using either a digital recording device or recorded directly onto a VA computer. Upon completion of all interviews, the recordings will be transferred to the secure shared network folder. The qualitative interviews will also allow us to modify the treatment in the future.

Assessment Instruments

a. Screening

The screening questionnaires will be used to determine inclusion and exclusion criteria. These questionnaires will be administered over the phone to determine a potential participant's eligibility, given exclusion and inclusion criteria, to enroll into the study. In addition to the listed questions we will ask potential participants about exclusionary medical and psychiatric conditions.

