These six life tasks reflect two underlying constructs: Activity limitations and Participation deficits. The WHO-DAS 2.0 is based off of the International Classification of Functioning, Disability and Health (ICIDH-2), which categorizes disability into three categories: physiological, activities and participation. The WHO-DAS 2.0 has been translated into 15 languages and tested in 13 countries. The six domains have a factor loading of 0.82 to 0.98 and all load onto the general disability factor. Participants will be asked to complete this at all time points. We will use the WHO-DAS 2.0 screener which is a 12 item measure at screening. The WHO-DAS 2.0 screener explains 86% of the variance in the full measure and will reduce burden at screening. As the WHO-DAS is the primary outcome measure, we will use the full, and more valid, 36 item measure during the study.

3. Columbia-Suicide Severity Rating Scale (C-SSRS): The C-SSRS is the gold standard for suicide assessment. It is used by the VAs Center of Excellence for Suicide Prevention. The C-SSRS was developed by Columbia University and is used extensively across primary care, clinical practice, surveillance, research, and institutional settings. The C-SSRS in one study showed 100% sensitivity and specificity in identifying individuals who attempted suicide. Across three major randomized controlled trials, the C-SSRS demonstrated convergent, divergent, and predictive validity; sensitivity to change; sensitivity and specificity of the instrument; and internal consistency of the intensity subscale. (Posner et al., 2011) is part of a national and international public health initiative involving the assessment of suicidality, including general medical and psychiatric emergency departments, behavioral health organizations, medical homes, community mental health agencies, primary care, clergy, hospices, schools, college campuses, US Army, National Guard, VAs, Navy and Air Force settings, frontline responders, substance abuse treatment centers, prisons, juvenile justice systems, and judges to reduce unnecessary hospitalizations. At the screening and 12th session visit, this questionnaire will be administered by a member of the research staff.

b. Questionnaires

The questionnaires described by construct below will be administered at certain time points. Questionnaires may be administered in person at baseline and after the 12th session.

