- van der Zee, C. H., Priesterbach, A. R., van der, D. L., Kap, A., Schepers, V. P., Visser-Meily, J. M. et al. (2010). Reproducibility of three self-report participation measures: The ICF Measure of Participation and Activities Screener, the Participation Scale, and the Utrecht Scale for Evaluation of Rehabilitation-Participation. *J.Rehabil.Med.*, 42, 752-757.
- Ware, J., Jr., Kosinski, M., & Keller, S. D. (1996). A 12-Item Short-Form Health Survey: construction of scales and preliminary tests of reliability and validity. *Med.Care*, 34, 220-233.

Summary List of Measures and Timeline

Domain	Study Instruments	# of Items	Screening	Baseline	4 week	12 week	24 week (6 month)
Screening	General Screening Questionnaire	27	X				
	Columbia Suicide Severity Rating Scale [C-SSRS]	26	X			X	
	Mini International Neuropsychiatric Interview [MINI]	23	X				
	World Health Organization Disability Assessment Schedule- 12 items [WHO-DAS]	12	X				
Estimated Completion Time for Screening Domain: 35-45 minutes							
Problem-Solving	Problem Solving Inventory [PSI]	32		X	X	X	X
	Behavioral Responses to Illness Questionnaire [BRIQ]	19		X	X	X	X
Estimated Completion Time for Problem-Solving Domain: 9 minutes							
Gulf War Illness	Fatigue Severity Scale [FSS]	9		X		X	X
	KANSAS Questionnaire [KANSAS]	29	X			X	
	Patient Health Questionnaire 15-items [PHQ-15]	15		X	X	X	X
	Pain Disability Inventory [PDI] & Pain Inventory [MPI]	10		X		X	X
	MOS Sleep Scale [MOS-Sleep] & Insomnia Severity Index [ISI]	19		X		X	
Estimated Completion Time for Gulf War Illness Domain: 16 minutes							
Disability	World Health Organization Disability Assessment Schedule- 36 items [WHO-DAS]	36		X	X	X	X
	Veterans RAND 12 Item Health Survey [VR-12]	12		X		X	
	USER-P (activity satisfaction and frequency) [USER-P]	21		X		X	X
	MOS Social Support [MOS-SS]	8		X		X	X
Estimated Completion Time for Disability Domain: 14 minutes							
Participant Characterization	Alcohol Use Disorders Identification Test Alcohol Consumption Questions [AUDIT-C]	4		X		X	
	Post Traumatic Stress Disorder Checklist [PCL-5]	20		X		X	X
	Patient Health Questionnaire 8 items [PHQ-8]	9		X		X	X
	Brief Traumatic Brain Injury [BTBIS]	4		X			
	Demographics [Demo]	30		X		X	X
	Healthcare Access [HCA]	17		X		X	X
Estimated Completion Time for Characterization Domain: 12 minutes							
Veterans Perceptions of Problem-Solving and Health Education	Working Alliance Inventory (Self) [WAI]	12			X	X	
	Target Complaints Questionnaire [GOALS]	6		X		X	

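### Exclusion (a) depends on current suicidal or homicidal intent, but no planned assessment establishes that status at allocation, and the scale it names is described as covering suicide only

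*Combined protocol and SAP*

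**What the plan says.** Study Population, Exclusion (a), removes Veterans with "current suicidal/homicide intent or plan assessed by The Columbia Suicide Severity Rating Scale, schizophrenia or current psychotic symptoms".

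Assessment Instruments, a. Screening, item 3, describes the scale: "The C-SSRS is the gold standard for suicide assessment". It gives the timing as: "At the screening and 12th session visit, this questionnaire will be administered by a member of the research staff". In the Summary List of Measures and Timeline, the row "Columbia Suicide Severity Rating Scale [C-SSRS]" has marks under Screening and 12 week and none under Baseline.

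On the mode of screening, Assessment Instruments says: "These questionnaires will be administered over the phone". Methods, a. Recruitment and Screening, also allows staff to "conduct initial screenings in person or over the phone" when the Veteran approaches the study. For a Veteran found eligible, "a date and time will be scheduled for the Veteran to come into one of the three study sites" for consent and baseline. No upper limit on the wait is given there or elsewhere.

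**The concern.** The criterion describes a state that can change over days or weeks, and the plan measures it before enrolment with nothing that fixes how long before. The scale is next given at session 12, when it can no longer inform eligibility. If a Veteran's state changes between screening and allocation, following the schedule exactly would allow that Veteran to be randomised. The protocol itself lists emotional distress from the questionnaires and phone sessions as a risk, so this exclusion matters for safety. It also matters for the record: eligibility documented at screening may be out of date at the point where it counts.

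A second, smaller problem lies in the wording. The criterion covers homicidal as well as suicidal intent and attaches both to the C-SSRS, but the protocol's description of that scale mentions suicide only.

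**Working it through.** No formula applies, and the plan states no figure to reproduce. The check sets the sections side by side.

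**Step 1. What is assessed, and when.**

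| Instrument or step | Screening | Baseline | After allocation | Relation to exclusion (a) |
|---|---|---|---|---|
| C-SSRS (26 items) | Yes | No | Session/week 12 | Named in the criterion; described as a suicide scale |
| MINI (23 items) | Yes | No | No | Psychiatric interview by its title in the reference list; content not described |
| General Screening Questionnaire (27 items) | Yes | No | No | Content not given |
| Added screening questions on psychiatric exclusions | Yes | None stated | None stated | Content not given |
| PHQ-8 | No | Yes | Weeks 12 and 24 | Depression measure, not linked to the criterion; 8 items in the text, 9 in the table |
| Mental health provider form | No | Yes | None stated | Documents that the Veteran was encouraged to talk to a provider |

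Four screening steps could bear on exclusion (a), and none is scheduled again before allocation. The two baseline rows are not tied to the criterion.

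**Step 2. Do text and table agree on C-SSRS timing?** Yes. Both give two administrations, at screening and at session/week 12, and none at baseline. The missing baseline entry is therefore not an extraction fault or an inconsistency between the two places.

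**Step 3. Is the interval bounded?** No maximum is stated from screening to baseline or from screening to randomisation. The period of about two weeks in Recruitment and Screening runs from the introduction letter to the first call. It precedes screening and bounds nothing afterwards. The day of randomisation relative to baseline is not stated. Recruitment may be national and may involve travel to a site, so a wait is plausible; a short gap is possible too.

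**Step 4. Who covers homicidal intent?** The criterion says the C-SSRS does. The C-SSRS description does not mention it. The MINI, the General Screening Questionnaire or the added questions might ask about it, but their content is not given and the criterion does not point to them.

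**Step 5. What a re-check would add to.** The table puts baseline at 70 minutes of questionnaires and 50 minutes of neuropsychological tests: 70 + 50 = 120 minutes.

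**The case against.** The best reply is that exclusion (a) still removes everyone who is positive at screening, that other instruments are in use, and that safeguards continue afterwards. The investigator may exclude for a psychiatric disorder that bears on safety. Baseline includes a mental health provider form. Primary care providers are told of participation and can raise concerns. The study may contact a Veteran's health care providers whenever safety is in question. Licensed or supervised providers ask about new health concerns during sessions. All of this stands and reduces the likely harm. But these are discretionary or passive, or they begin after allocation, and none re-establishes the criterion.

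It can also be said that the gap may be short, and that the timing of the scale is a choice rather than a contradiction. Both are fair. The plan does not ensure a short gap, however, and a consistent schedule can still leave a current-state criterion unverified.

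Some stronger readings are tempting but not supported:

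- *The exclusion protects nobody, or ineligible Veterans will be randomised.* It works at screening. The documents support only that such a Veteran could be randomised.
- *The C-SSRS is the only psychiatric screening instrument.* It is the only one that exclusion (a) names. The table also lists "Mini International Neuropsychiatric Interview [MINI]" and a General Screening Questionnaire, and the text adds psychiatric questions.
- *Psychosis is assigned to the C-SSRS.* In the criterion, schizophrenia and psychotic symptoms follow a comma and stand outside the phrase naming the scale. Only the homicide wording is misattached.
- *The gap is 14 to 20 weeks.* That would be the time between the two C-SSRS administrations under an assumed scheduling delay of 2 to 8 weeks (2 + 12 = 14; 8 + 12 = 20). Twelve of those weeks follow allocation, so this is the wrong interval, and no section supports the assumed delay.
- *The ninth PHQ item in the table closes the gap, or shows an error.* Its content is not shown, so nothing follows either way.

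**Conclusion.** The point holds in this form: current status under exclusion (a) is not established at allocation by any planned assessment, and the criterion assigns homicidal intent to a scale the protocol describes as a suicide assessment.

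The size cannot be put in numbers. The screening-to-allocation interval is not stated, and neither is the rate at which Veterans' status changes, so no count can be derived from the planned maximum of 300. No effect on power, type I error or the primary analysis follows. The consequence is for participant safety and for the validity of recorded eligibility.

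The conclusion rests on reading *current* as applying at enrolment, and on the documents being complete about when the screening instruments are given. If randomisation in practice follows screening within a very short time, the gap is small, but the plan would still need to say so. Because the schedule as written permits the event and the remedy is cheap, the point deserves a change before further enrolment rather than a note.

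**What to change.** Reconcile Study Population (Exclusion (a)), Recruitment and Screening, the C-SSRS description and the Summary List of Measures and Timeline, so that they say when current status is established and make that point allocation. Two examples would do it:

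- Confirm the existing exclusion (a) items at the consent/baseline contact, before allocation. Because baseline questionnaires may be completed by mail or phone, tie the check to the consent contact or make it by phone, so that it is uniform.
- State a screening-to-allocation window, its length chosen by the investigators, after which screening on these items is repeated.

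In Exclusion (a), name the screening instrument that actually asks about homicidal intent. While editing, state when randomisation occurs relative to baseline.

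The cost is an entry in the measures table, some wording, a few minutes of staff time beside a baseline of about 120 minutes, and possibly some late screen failures. Staff already give the scale at screening. How a positive answer is managed is for the investigators.

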Participants will be given or mailed a Health Education workbook after the baseline assessment. For participants enrolled at the Bedford VA and Canandaigua VA, the Study Coordinator from the East Orange VA may mail the Health Education workbook. The Health Education workbook will be used in conjunction with the sessions. The content in the Health Education workbook includes didactic information on a variety of health topics pertinent to GWVs, i.e., pain, improving cognition, sleep, diet and physical activity. This information will also be reviewed with the Study Provider during each session. Similar to those randomized to the PST group, at the Study Provider's or PI's discretion, the Health Education protocol may vary in order to meet a Veteran's needs (e.g., changing the order of the information given, having an additional session if feasible).

Participants who are assigned to the health education control condition may be offered the 12-session PST program at the end of the study.

During the sessions, participants will regularly be asked questions on their perception of the sessions, treatment and if they have any new health concerns.

Reducing Attrition

To reduce attrition and the burden on the Veteran, all therapy sessions are done over the phone or video to phone if available. In addition, we plan to make phone calls to remind participants about their scheduled appointments (similar to the VA's automated appointment reminder system). PST has been successfully implemented over the telephone. Prior to starting the treatment, the participant and Study Provider may determine the time that is best for the Veteran (including nights and weekends) and may determine ground rules (for example, not having anyone else in the room, shutting off other telephones to remove distractions). The Study Provider and Veteran may also establish verbal signals to substitute for non-verbal cues, for example, "that's great" or "can I interrupt."

Participants will be allowed to begin or continue with their existing medical regimen throughout the course of the trial and make changes to their existing treatments. Adherence to medical protocols and participation in alternate treatments will be evaluated by a questionnaire at the assessments and this will be controlled for in analyses. The Study Provider may make additional recommendations for additional health care if needed or as appropriate.

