11. Behavioral Responses to Illness Questionnaire (BRIQ): The BRIQ was developed to assess how individuals problem-solve medically unexplained symptoms. Internal reliability is above .80, test-re-test reliability is acceptable (.60-.87) and it is able to predict the onset of medically unexplained symptoms (Spence et al., 2005).
12. Demographic Survey & Healthcare Access: This is a brief questionnaire designed to elicit basic demographic information including: sex, age, marital status, self-identified racial and ethnicity group, educational level, income level, sources of current income, and current employment status, health insurance and health care utilization. The information obtained through this survey will be used to assess demographic differences between groups and identify potential control variables. We will also ask for self-report of medical conditions and medication.
13. The Brief Traumatic Brain Injury Screen (BTBIS): The VA/DOD BTBIS assesses TBI by asking if the participant has had an injury and if the injury resulted in a symptom. It will be used as a control variable in analyses.
14. Patient Health Questionnaire (PHQ-8): The PHQ is a self-administered questionnaire yielding algorithmic diagnoses of psychiatric illness. It was specifically developed and validated for use in primary care settings. We will administer the 8 item depression questionnaire. Patients are instructed to code each symptom based on whether it bothered them over the preceding 2 weeks: “not at all”, “several days”, “more than half the days”; or “nearly every day”. Depression is a common comorbid condition among Gulf War Veterans with Gulf War Illness.
15. Post Traumatic Stress Disorder Checklist (PCL): The 21 item National Center for PTSD Checklist of the VA will be used to assess PTSD. When compared to the gold standard for assessing PTSD, the Clinician Administered PTSD scale (CAPS), the PCL has been shown to be a valid and reliable measure of PTSD symptoms. PTSD is a common comorbid condition among Gulf War Veterans with Gulf War Illness.
16. Alcohol Use Disorders Identification Test (AUDIT-C): a 4-item alcohol screen used to identify patients with hazardous drinkers or have alcohol use disorders. The AUDIT is used in the VA to screen patients with alcohol use disorders.

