Data analyses will be conducted both on-site by study investigators and with proper approvals, including DUAs, at our affiliate institutes by current and future study investigators. All analyses will be primarily performed on an intention-to-treat basis. The statistical significance will be defined by a p value < 0.05 , unless specified otherwise. Calculations of the means, standard deviations, proportions, histograms, etc., will be conducted to explore the distributions of the data, identify outliers, and calculate correlations between variables. We will also determine confounders that need to be controlled for in our analyses. We will particularly examine if we need to control for depression measured with the PHQ-8 or PTSD symptoms measured with the PCL based characteristics that exhibit differences at the baseline (pre-intervention).

Due to repeated measures, we will analyze the data using mixed model analysis, with participants nested within therapists modeled by random effects. To address H1, disability (WHODAS II scores) will be treated as the dependent variable, and treatment assignment [PST vs. Health education], time [pre- vs. post-intervention] and their interaction will be modeled as fixed effects. Differences in the improvement of disability between Problem-solving therapy and Health education will be evaluated by the treatment by time interaction. Linear contrasts will be constructed to evaluate the improvement in disability for each treatment separately. Variables such as age, gender, education and the confounders identified in the preliminary analysis will be controlled as covariates in the statistical analyses. Data transformations (e.g., square root, log,

etc.) will be used to normalize data where necessary. The same mixed model analysis strategy will be applied to address H2a, H2b, H3a and H3b. We will also explore, using this same mixed model strategy, the impact of PST therapy on each of the four individual neuropsychological tests scored as a composite and scored individually (Category Test, CPT 3, Stroop Test, and TMT). We will use the same data analysis strategy to examine all secondary outcomes. These will be reported as secondary outcomes and will primarily be used to generate hypotheses.

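### H1 covariates are chosen from observed baseline differences, with no threshold and an open list; the list should be fixed before arm-level data are seen

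*Combined protocol and SAP*

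**What the plan says.** All references are to the combined protocol and SAP.

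- **Data Analysis, a. Data** opens a general search: "We will also determine confounders that need to be controlled for in our analyses". It singles out "depression measured with the PHQ-8 or PTSD symptoms measured with the PCL based characteristics that exhibit differences at the baseline (pre-intervention"). The models then take up the result: "Variables such as age, gender, education and the confounders identified in the preliminary analysis will be controlled as covariates in the statistical analyses". Age, gender and education are introduced only as examples.
- **The H1 model** in the same section is a mixed model of WHO-DAS in which "treatment assignment [PST vs. Health education], time [pre- vs. post-intervention] and their interaction will be modeled as fixed effects". Baseline WHO-DAS is therefore one of the responses, and H1 is judged by the treatment-by-time interaction.
- **Questionnaires, item 12** says the demographic information "will be used to assess demographic differences between groups and identify potential control variables".
- **Questionnaires, item 13** says of the traumatic brain injury screen (BTBIS): "It will be used as a control variable in analyses". This has no imbalance condition.
- **Reducing Attrition** says adherence and use of other treatments "will be evaluated by a questionnaire at the assessments and this will be controlled for in analyses".

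None of these places states a test, a cut-off, a closed set of candidates, a date for the decision, or a default model if nothing is identified.

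**The concern.** Allocation is randomised, so a baseline difference between arms is chance. Its size does not show how strongly the variable predicts WHO-DAS, which is the reason to adjust in a trial. A rule that uses imbalance therefore selects on the wrong criterion.

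The rule also needs arm-level baseline data before the model is known. With no threshold and an open list, two analysts could follow the plan and fit different H1 models. The plan foresees analysis at several institutions by present and future investigators, so this could happen. At stake are the reproducibility of the H1 result and its protection from choices made after the data are seen.

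**Working it through.** The plan states no power, effect size, SD or dropout figure, so there is no figure of its own to reproduce.

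**Inputs from the plan.** Up to 300 Veterans (Study Population); two randomised arms, ratio not given; p < 0.05; H1 tested by treatment by time.

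**Assumed for illustration.** 150 per arm; two-sided test; SD 1 at each time; effect 0.3 SD; pre-post correlation 0.6; covariate correlation with WHO-DAS between 0.3 and 0.5; post-treatment missingness 0, 20 or 30%. The therapist random effect is left out.

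**1. How often would the rule omit a variable?** It depends on a threshold the plan does not give.
- Screen at p < 0.05: each variable is omitted 95% of the time. PHQ-8 and PCL are both omitted in 0.95² = 90.3% of trials if independent, and 92.2% if correlated 0.8.
- Standardised difference above 0.1, N = 300: the standard error is √(4/300) = 0.1155 and 0.1/0.1155 = 0.866, so each is omitted with probability 0.614. Both are omitted in 0.614² = 38% of trials if independent. The bivariate normal probability at correlation 0.8 is 0.475, still below half.

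**2. Complete pre and post data, covariate as a main effect.** The interaction estimate is (mean change in PST) − (mean change in health education). A term βx takes the same value at both times for each person, so it drops out of every change.
- Closed form: Var(change) = 2(1 − 0.6) = 0.8; SE = √(0.8 × 4/300) = 0.1033; power = Φ(0.3/0.1033 − 1.96) = 0.83.
- Simulated random-intercept REML fits (400 runs) agree: SE 0.1032, power 0.83. Adding the covariate moved no estimate by more than 4 × 10⁻¹⁶ and no SE by more than 5 × 10⁻⁹. No verdict changed in 400.

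**3. When the choice does matter.** The table gives the share of 400 runs in which significance differs between the model without the covariate and the model with it. Missingness depends on the covariate in the same direction in both arms.

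| Post data missing | Correlation with WHO-DAS, pre / post | Added as main effect | Added by time |
|---|---|---|---|
| 0% | 0.5 / 0.5 | 0% | 1.5% |
| 0% | 0.5 / 0.3 | 0% | 4.5% |
| 20% | 0.5 / 0.5 | 2.5% | 2.75% |
| 20% | 0.5 / 0.3 | 3.5% | 6.5% |
| 30% | 0.5 / 0.5 | 5.0% | 5.5% |

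Monte Carlo error at 5% is √(0.05 × 0.95/400) = 1.1 points. With main effects and missing data, the mean absolute shift in the estimate is about 0.01 to 0.015 SD. In a constructed worst case, with 25% missing and dependence on the covariate in opposite directions by arm, the shift was about 0.06 SD.

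**4. Type I error.**
- One covariate, p < 0.05 screen applied mechanically, 4,000 runs (Monte Carlo SE about 0.0034): 0.046 to 0.051 for the change score and 0.040 to 0.054 for ANCOVA.
- Upper bound on discretion: the smallest p over all subsets of two or three covariates entered by time (mutual correlation 0.5) gives 5.7 to 5.8% if each correlates 0.1 with change, and 7.6 to 8.3% at 0.3.

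**5. Adding baseline WHO-DAS as a covariate to this model.** The same value is then both a response and a predictor. The intercept variance goes to zero, and the interaction SE shrinks by √((3 + r)/4), where r is the pre-post correlation. For r = 0.4, 0.6 and 0.8 the factor is 0.922, 0.949 and 0.975. The type I error, 2(1 − Φ(1.96 × factor)), is 0.071, 0.063 and 0.056. Simulations gave about 0.056 to 0.074.

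**The case against.** The strongest reply is that the planned test barely feels the choice. A main-effect baseline covariate cancels from the treatment-by-time contrast, a mechanical screen holds its 5% level, and age, gender, education and BTBIS are named without an imbalance condition. Most of this stands, and it rules out several stronger readings.

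- **A sizeable bias or loss of precision.** A reader might reason that a difference just short of p < 0.05 is 1.96 × √(2/150) = 0.226 SD. At a correlation of 0.3 with follow-up WHO-DAS that leaves 0.226 × 0.3 = 0.068 SD, or 23% of a 0.30 SD effect, and adjustment would remove 0.3² = 9% of variance. That is the arithmetic of a follow-up-only comparison or an ANCOVA. It does not describe the H1 test.
- **Prognostic variables usually left out.** This needs a significance-type cut-off that the plan does not give. The plan calls depression and PTSD common comorbid conditions, but gives no evidence that they predict WHO-DAS.
- **An inflated error rate.** Step 4 shows none for a mechanical rule. The 5.7 to 8.3% is a worst case for free choice, not a forecast.
- **A contradiction over BTBIS.** The analysis section lists its covariates as examples, so item 13 is compatible with it.

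The reply does not reach the rule itself. The plan does not restrict covariates to main effects, it anticipates attrition, and its rule is not mechanical.

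**Conclusion.** The point holds as a cheap improvement. The plan states an imbalance-based rule for the primary model, with no threshold and an open list, and a fixed list is a better method. The effect on H1 is nil for main-effect covariates with complete data. In the missing-data and by-time settings simulated, 1.5 to 6.5% of verdicts changed. Those figures rest on the assumed effect, correlations and missingness, for one covariate at a time and without the therapist effect. Missingness related to the covariate in opposite directions by arm would move the estimate more. The documents do not support a claim of bias, of type I inflation from a mechanical screen, or of a stated power loss.

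**What to change.** Delete the imbalance-based selection in Data Analysis and the matching purpose in the demographic survey entry. Before arm-level data are seen:

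- Fix the H1 covariates as age, gender, education, baseline PHQ-8, baseline PCL, BTBIS and study site, included whatever the imbalance.
- State for each whether it enters as a main effect or by time.
- Do not add baseline WHO-DAS as a covariate while it remains the pre-intervention response.
- Report baseline differences descriptively, without tests.
- Label any other covariate set a sensitivity analysis.
- Say whether the adjustment for adherence and other treatments applies to H1, since values recorded after baseline are post-randomisation.

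Cost: SAP wording. With one term each for the first six and two for three sites, the list uses 6 + 2 = 8 degrees of freedom as main effects. Four of these (PHQ-8, PCL and site) are beyond what the plan already names. All these variables are already recorded by baseline.
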